5 STUDY PROCEDURES

5.1 Screening Visit

The following procedures will be performed prior to the first laser treatment for both types of laser treatments:

1. Informed consent.
2. Investigator assessment of treatment area for study eligibility.
3. Review of medical history.
4. Subject will be randomly assigned to either the Enlighten cohort or the Excel V cohort.
5. Assessment of concomitant medications.
6. Pre-treatment digital photographs of the subject’s treatment area will be taken.
7. Provide and explain the before / after treatment instructions to the subject.

Once it has been determined that the subject meets all criteria to be included in the study and informed consent has been obtained, the subject will be enrolled in the study.

5.2 Laser Treatment Visit(s)

[Redacted text block]

[Redacted text block]

Table 1 [Redacted]

[Redacted]	[Redacted]	[Redacted]
[Redacted]	[Redacted]	[Redacted]
[Redacted]	[Redacted]	[Redacted]
[Redacted]	[Redacted]	[Redacted]
[Redacted]	[Redacted]	[Redacted]

[Redacted text block]

[Redacted]	[Redacted]	[Redacted]
[Redacted]	[Redacted]	[Redacted]
[Redacted]	[Redacted]	[Redacted]
[Redacted]	[Redacted]	[Redacted]
[Redacted]	[Redacted]	[Redacted]
[Redacted]	[Redacted]	[Redacted]

9. [REDACTED]
[REDACTED]
[REDACTED]
[REDACTED]

[REDACTED]
[REDACTED]
[REDACTED]
[REDACTED]
[REDACTED]
[REDACTED]

5.3 Final Follow-Up Visit

The follow-up visit will occur at approximately 4 weeks [REDACTED].

The following procedures will be performed at the follow-up visit:

1. Assessment of concomitant medications: Assess and record any additions, changes and/or deletions in prescription and nonprescription concomitant medications since the previous study visit.
2. Assess for any new procedure related adverse effects or changes to previously recorded adverse effects.
3. Digital photographs of the treated area(s) will be taken.
4. [REDACTED] Physician's Global Assessment of Improvement
5. Subject will be asked to complete and return the Subject Questionnaire.

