12 SUBJECT CONFIDENTIALITY16

13 PUBLICATION POLICY17

REFERENCES.....18

Protocol Summary

Title	A Single-Center 2-Arm Study of the Enlighten and Excel V Laser for Lentiginos on the Hands
Objective	
To evaluate the effectiveness and safety in a clinic setting of two laser systems for improvement of lentiginos on the hands:
 
 1. Cutera Enlighten [REDACTED] 2. Cutera Excel V [REDACTED]
Study Design	A single-center prospective, open-label, 2-armed uncontrolled study.
Enrollment	Up to 12 subjects in each arm
Primary Endpoint	
 • Reduction of the number of lentiginos at 4 weeks [REDACTED] post-final treatment [REDACTED]
Secondary Endpoints	
 • Degree of improvement in [REDACTED] skin texture, and overall appearance of the hands at 4 weeks [REDACTED] post-final treatment. • Subject satisfaction at 4 weeks [REDACTED] post-final treatment. • Incidence and severity of adverse effects during the study period [REDACTED]
Subject Population	Female or male subjects, age 30 to 90 years, Fitzpatrick skin types I-III
Planned Schedule	
First subject enrolled: April 2016
 
Last subject last visit: June 2016 (Enlighten cohort)
 
October 2016 (Excel V cohort)

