2 STUDY PURPOSE AND OBJECTIVES

The purpose of this study is to evaluate the effectiveness and safety in a clinic setting of two laser systems for the treatment of lentigines (liver spots, age spots, or dark sun spots) on the hands:

- Cutera Enlighten dual wavelength 532 nm [REDACTED] and/or 1064 nm Nd: YAG picosecond pulse duration laser
- Cutera Excel V dual wavelength 532nm [REDACTED] long pulsed laser and/or 1064 nm Nd: YAG

The objectives of this study are to:

- 1) Evaluate the reduction of the number of lentigines on the hands, the improvement of [REDACTED] skin texture, and overall appearance, and customer satisfaction 4 weeks following treatment with one of the two study lasers.
- 2) Evaluate the rate of adverse events experienced by the study subjects.

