3.1.2 Secondary Endpoints

- Degree of improvement in skin texture of the hands at 4 weeks [REDACTED] post-final treatment as assessed by a [REDACTED] physician using the Physician’s Global Assessment scale.
- Degree of improvement in overall appearance of the hands at 4 weeks [REDACTED] post-final treatment as assessed by a [REDACTED] physician using the Physician’s Global Assessment scale.
- Subject satisfaction at 4 weeks [REDACTED] post-final treatment.
- Incidence and severity of adverse device effects during the study period

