6.1 Reporting of Adverse Events

If any serious adverse event (SAE), anticipated or unanticipated, occurs at any time during or after the use of the device within the study period, the investigator must report it to Cutera within 24 hours using the Cutera Serious Adverse Event Report Form.

If the SAE is unanticipated in nature, severity or degree of incidence, Cutera will notify all events that fulfill the following criteria to the Institutional Review Board (IRB) within ten (10) working days using the IRB Unanticipated Problem/Event Report Form:

- **Serious** (i.e., death, a life-threatening adverse experience, inpatient hospitalization or prolongation of existing hospitalization, a persistent or significant disability or incapacity, or a congenital anomaly or birth defect) [21 CFR 312.32(a)], **AND**
- **Unexpected** (i.e., not described in the Informed Consent Document), **AND**
- **Related** to the study design, procedures, or device (possibly, probably or definitely related, or unknown).

OR

- Any event that, in the opinion of the investigator, may adversely affect the rights, welfare or safety of subjects in the study.

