6.2 Follow-up of Subjects after AEs

All reported AEs should be followed until resolution or until the subject's participation in the study ends. All AEs assessed by the investigator as probably related or possibly related to the study device should be followed until they resolve or until the investigator assesses them as "chronic" or "stable". Resolutions of such events are to be documented on the appropriate CRF pages. All AEs that result in permanent discontinuation from this clinical trial, whether serious or not, should also be reported on the Subject Non-Completion of Study Form.

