9.2 Data Analysis

Descriptive statistics and 95% confidence intervals and will be calculated for percent reduction in the number of hand lentigines, at 4 weeks [REDACTED]

Descriptive statistics and 95% confidence intervals and will be calculated separately for improvement in skin texture, and overall appearance of the hands, based on the Physician's Global Improvement Assessment evaluation, and also for the Subject Satisfaction Scale evaluations.

Safety measures include the incidence of treatment-related AEs, the proportion of subjects who prematurely terminate from the study due to a treatment-related AE [REDACTED]

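### Objective 2 covers all adverse events, but the final visit asks for new events only if procedure related, so that visit cannot supply an all-AE rate

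*Combined protocol and SAP*

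**What the plan says.** The safety question is worded differently in each place where it appears.

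- Section 2, Objective 2: "Evaluate the rate of adverse events experienced by the study subjects".
- Protocol Summary, Secondary Endpoints: "Incidence and severity of adverse effects during the study period".
- Section 3.1.2: "Incidence and severity of adverse device effects during the study period".
- Section 5.3, item 2 (final visit): "Assess for any new procedure related adverse effects or changes to previously recorded adverse effects".
- Section 9.2: "Safety measures include the incidence of treatment-related AEs, the proportion of subjects who prematurely terminate from the study due to a treatment-related AE", after which the sentence runs into a redaction.

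Three readable rules are not limited by cause. Section 6.1 begins "If any serious adverse event (SAE), anticipated or unanticipated, occurs at any time during or after the use of the device" and requires a report to the sponsor within 24 hours. Section 6.2 says "All reported AEs should be followed until resolution or until the subject's participation in the study ends", and then sets a longer follow-up rule for AEs that the investigator considers probably or possibly related to the device. Section 6.2 also sends every AE that causes permanent discontinuation, serious or otherwise, to the non-completion form.

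Section 3 describes the study as open-label and uncontrolled. Section 5.2 (treatment visits), Section 6 before 6.1, Section 11 (data collection) and the end of the safety sentence in 9.2 are redacted.

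**The concern.** A rate of all adverse events needs all adverse events to be asked for. Section 5.3 puts a causality judgment in front of the question: for a new event, the site is prompted only if someone already thinks the procedure caused it. The usual order is to record first and grade causality afterwards, so that the grading can be reviewed.

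Two things are at stake. First, the final visit cannot feed the rate that Objective 2 names. Second, the two kinds of attribution error are treated unequally. An event wrongly called related is on record and can be corrected. An event wrongly called unrelated may not be on record, and so might not be available for re-grading. The person making the judgment knows which laser was used.

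**Working it through.** The plan states no AE rate and no share of events judged unrelated, so there is no figure to reproduce. The check is a comparison of texts, with one illustrative calculation.

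**Step 1. Scope in each place.**

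| Place | Events covered | Limited by cause? |
|---|---|---|
| Section 2, Objective 2 | adverse events | no |
| Protocol Summary | adverse effects | not stated |
| Section 3.1.2 | adverse device effects | yes, device |
| Section 5.3, item 2, new events | adverse effects | yes, procedure |
| Section 5.3, item 2, events already recorded | changes | no |
| Section 9.2, readable part | AEs, and terminations due to them | yes, treatment |
| Section 6.1, report to sponsor | SAEs | no |
| Section 6.2, non-completion form | AEs causing permanent discontinuation | no |

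The limiting term also changes: procedure in 5.3, treatment in 9.2, study device in 6.2. For IRB notification, Section 6.1 counts unknown relatedness with related. The 5.3 item gives no place for unknown.

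**Step 2. Follow an event first mentioned at the final visit through the readable text.**

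1. Serious: captured under 6.1, whatever the cause.
2. Causes permanent discontinuation: captured under 6.2, whatever the cause.
3. Neither, and judged procedure related: asked for under 5.3.
4. Neither, and judged unrelated: not asked for under 5.3, and not among the measures that can be read in 9.2.

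A change to an effect already recorded is asked for under 5.3 with no causality limit. The demonstrable gap is therefore case 4 alone.

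**Step 3. What one subject is worth.** Inputs: up to 12 per arm (Protocol Summary) or up to 24 per arm (Sections 3 and 9.1). This conflict is a separate matter, so both sizes are shown. One subject is 100/12 = 8.3 percentage points or 100/24 = 4.2 percentage points. Starting from an assumed 25% of subjects with an event, with exact (Clopper-Pearson) 95% intervals:

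| Arm size | All counted | One subject missed |
|---|---|---|
| 12 | 3/12 = 25.0% (5.5 to 57.2%) | 2/12 = 16.7% (2.1 to 48.4%) |
| 24 | 6/24 = 25.0% (9.8 to 46.7%) | 5/24 = 20.8% (7.1 to 42.2%) |

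The 25% is an assumption for illustration; nothing in the documents supports or contradicts it. The change per missed subject does not depend on it.

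**The case against.** The strongest reply is that Sections 5.3 and 9.2 broadly fit the endpoint as Section 3.1.2 defines it. If the study is about device effects, asking for procedure-related effects and analysing treatment-related AEs is coherent, and Objective 2 is the outlier. This stands as an account of where the mismatch may come from. It does not remove the mismatch, because Objective 2 is stated without that limit.

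A reader might infer that unrelated events need never be recorded in this study. The documents do not support that. SAEs and discontinuing AEs are captured whatever their cause. Section 6.2 treats all reported AEs and related AEs separately, which implies that unrelated ones can be on record. Section 5.2, the opening of Section 6 and Section 11 are redacted and may hold a general all-AE rule. Section 9.2 says that its measures include those listed and then breaks off, so the readable list is not shown to be complete.

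A reader might also multiply an assumed device-effect rate by an assumed share wrongly judged unrelated, to get a bias for the whole study. Neither number is in the documents, and the rule in 5.3 touches only events new at the final visit. Nor do attribution errors work in one direction only: calling an unrelated event related raises the related-event rate. Finally, the open-label design bears on who judges causality. The readable part of 9.2 plans no between-arm comparison of AEs that it would distort.

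**Conclusion.** The point holds in a limited form. The objective, the endpoint, the final-visit item and the readable analysis use different AE scopes. On the readable text, a new, non-serious, non-discontinuing event judged unrelated is not asked for at the final visit. That visit therefore cannot supply the all-AE rate of Objective 2, and an under-attributed event might be unavailable for later re-grading. Whether such an event is lost for good cannot be said, because the general recording rule may lie in redacted text. If it does, Section 5.3 conflicts with it and the two need reconciling.

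The size cannot be estimated from the documents. Each missed subject costs about 8 points in an arm of 12 and about 4 in an arm of 24, both small against the width of the intervals. The final visit is the only post-treatment visit whose procedures can be read; its weight relative to the treatment visits is unknown. A change of wording is warranted.

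**What to change.** Change Section 5.3, item 2, to ask for every new adverse event whatever its suspected cause, together with changes to events already on record, and have the investigator grade causality after the event is recorded. In Section 9.2, report for each laser arm the number and percent of subjects with (a) any AE and (b) a treatment-related AE, each with an exact 95% confidence interval. Use the same terms in the Protocol Summary and Section 3.1.2, and check that the redacted recording rules agree.

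If the sponsor wants device effects only, the alternative is to narrow Objective 2 to them. That settles the wording but leaves the causality judgment ahead of recording.

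The cost is an edit to a few lines and a few more AE entries. The total AE rate will be higher than the related-only rate; reporting the two side by side makes clear why.

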6 ADVERSE EVENTS

[REDACTED]
[REDACTED]
[REDACTED]

[REDACTED]
[REDACTED]
[REDACTED]
[REDACTED]

[REDACTED]
[REDACTED]
[REDACTED]
[REDACTED]
[REDACTED]

[REDACTED]

6.1 Reporting of Adverse Events

If any serious adverse event (SAE), anticipated or unanticipated, occurs at any time during or after the use of the device within the study period, the investigator must report it to Cutera within 24 hours using the Cutera Serious Adverse Event Report Form.

If the SAE is unanticipated in nature, severity or degree of incidence, Cutera will notify all events that fulfill the following criteria to the Institutional Review Board (IRB) within ten (10) working days using the IRB Unanticipated Problem/Event Report Form:

- **Serious** (i.e., death, a life-threatening adverse experience, inpatient hospitalization or prolongation of existing hospitalization, a persistent or significant disability or incapacity, or a congenital anomaly or birth defect) [21 CFR 312.32(a)], **AND**
- **Unexpected** (i.e., not described in the Informed Consent Document), **AND**
- **Related** to the study design, procedures, or device (possibly, probably or definitely related, or unknown).

OR

- Any event that, in the opinion of the investigator, may adversely affect the rights, welfare or safety of subjects in the study.

6.2 Follow-up of Subjects after AEs

All reported AEs should be followed until resolution or until the subject's participation in the study ends. All AEs assessed by the investigator as probably related or possibly related to the study device should be followed until they resolve or until the investigator assesses them as "chronic" or "stable". Resolutions of such events are to be documented on the appropriate CRF pages. All AEs that result in permanent discontinuation from this clinical trial, whether serious or not, should also be reported on the Subject Non-Completion of Study Form.

7 POTENTIAL RISKS / BENEFITS

7.1 Potential Risks

[REDACTED]

7.2 Potential Benefits

The subjects may or may not benefit from the treatment. There is no guarantee of success.

7.3 Risk Management

The investigator participating in this study was chosen based on extensive and safe experience with the use of lasers in dermatology applications. This is the most critical element in managing subject risk. In addition, study investigators will be trained on the use of both the Cutera Enlighten and Excel V laser systems by a representative of Cutera.

8 TRAINING AND MONITORING

[REDACTED]

9 DATA ANALYSIS PLAN

9.1 Sample Size Calculation

The planned sample size of up to 24 subjects for each laser cohort was determined based on clinical judgment to provide sufficient information to evaluate reduction in the number of lentigines in the hands.

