3 STUDY DESIGN

This is a single-center prospective, 2-armed, open-label, uncontrolled study in up to 24 male or female subjects per arm, age 30 to 90 years who desire non-ablative laser treatment for treatment of lentigines of the hand, and additionally to evaluate the improvement of skin texture, and overall appearance of the skin.

Subjects will be assigned to a treatment arm using a random number generator.

[REDACTED]

Subjects will be instructed to maintain the same skin care regimen as before enrollment in the study, use daily sunscreen on the hands of SPF 50 or higher as approved by the study doctor and practice strict, diligent prevention of sun exposure.

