3.5 Study Discontinuation

The sponsor (Cutera, Inc.) has the right to terminate this study at any time. Reasons for terminating the study may include, but are not limited to, the following: incidence or severity of adverse events in this or other studies indicates a potential health hazard to subjects; subject enrollment is unsatisfactory; number of protocol deviations is unacceptable; data recording is inaccurate or incomplete; or questionable study site compliance with ICH-E6, Good Clinical Practice.

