4 STUDY POPULATION

4.1 Study Subject Recruitment and Selection including procedures for randomization

[REDACTED] male or female subjects who desire laser treatment for lentigines on the hand(s) will be studied for each of the laser treatments. Subjects will be recruited to participate from the local population. Subjects may also be recruited from the investigator’s existing patient database or from patients who present themselves to the study site requesting treatment. Only subjects who meet all eligibility criteria and who provide written informed

consent will be enrolled into the study. After verification of eligibility, there will be randomization into one laser group.

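### The stated enrolment maximum is 12 per arm in the Protocol Summary but 24 per arm in Sections 3 and 9.1

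*Combined protocol and SAP*

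**What the plan says.** Three places in the visible text set a maximum, and each says whether the number is per arm:

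- Protocol Summary, Enrollment row: "Up to 12 subjects in each arm".
- Section 3, Study Design: "up to 24 male or female subjects per arm".
- Section 9.1, Sample Size Calculation: "The planned sample size of up to 24 subjects for each laser cohort was determined based on clinical judgment". The sentence goes on to give the purpose of that number: "to provide sufficient information to evaluate reduction in the number of lentigines in the hands".

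Section 4.1 also gives a number of subjects who "will be studied for each of the laser treatments", but the number itself is redacted. Section 9.2 plans descriptive statistics with 95% confidence intervals for the efficacy measures, and incidence figures for safety. The visible text contains no hypothesis test, no power calculation and no statement of the total number of subjects.

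**The concern.** One arm cannot have a maximum of both 12 and 24. A maximum tells the site when to stop enrolling, and here the answer depends on which page is read. A 13th subject in an arm is within Sections 3 and 9.1 but over the limit in the Summary, so the visible text does not settle whether that enrolment is a protocol deviation. Section 3.5 names an unacceptable number of deviations among the possible reasons for ending the study, although nothing there refers to enrolment above a cap.

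The rationale is also affected. Section 9.1 rests on clinical judgment alone, and that judgment was expressed about 24. If 12 is the intended figure, the claim of sufficient information was made for a number twice as large, and no visible text supports 12.

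Finally, n determines what a descriptive study of this kind can show. It fixes the largest possible denominator for the safety incidences and the best precision available for the intervals in Section 9.2.

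**Working it through.** There is no sample-size formula to reproduce. Section 9.1 gives no alpha, power, effect size, SD or dropout rate. The check is therefore a comparison of the statements, followed by arithmetic on what the difference means.

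**Comparison**

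| Place | Unit | Maximum | Implied two-arm maximum |
|---|---|---|---|
| Protocol Summary, Enrollment row | each arm | 12 | 2 × 12 = 24 |
| Section 3 | per arm | 24 | 2 × 24 = 48 |
| Section 9.1 | each laser cohort | 24 | 2 × 24 = 48 |
| Section 4.1 | each laser treatment | redacted | – |

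The number of arms (two) is stated in the Summary and in Section 3. The totals are my multiplication. The ratio is 24/12 = 2. The disputed places are 24 − 12 = 12 per arm, or 2 × 12 = 24 over both arms.

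**Illustration of the effect on precision.** This assumes that each cap is filled and that every subject is evaluable. The visible text names no interval method, so the methods below are also assumptions.

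- *One subject with an event, as a share of the arm:* 1/12 = 8.3%; 1/24 = 4.2%.
- *Exact (Clopper-Pearson) two-sided 95% upper limit when no events are seen, 1 − 0.025^(1/n):* 26.5% at n = 12; 14.2% at n = 24. The one-sided 95% version, 1 − 0.05^(1/n), gives 22.1% and 11.7%.
- *95% half-width for a mean from a t-interval, t(0.975, n − 1)/√n, in SD units:* 2.2010/3.4641 = 0.635 at n = 12; 2.0687/4.8990 = 0.422 at n = 24. The ratio is 1.505, so the interval at 12 is about one and a half times as wide.

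**The case against.** The strongest reply is that the conflict does little harm. Both numbers are upper limits, so neither fixes n, and 12 or fewer subjects per arm complies with every statement. With no test, no power claim and no visible between-arm comparison, no planned inference depends on which cap is correct. The intervals will reflect the subjects actually studied. This stands, and it limits the weight of the point. It does not remove the point, because the plan still gives two answers for the 13th to 24th subject in an arm.

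A second reply is that 24 may be the two-arm total, since 2 × 12 = 24, wrongly labelled as per arm and then repeated. That is plausible but unproven. On that reading, Sections 3 and 9.1 are both wrong and need correction. Equally, agreement between two sections does not prove that 24 is intended, since one error may have been copied.

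The redacted number in Section 4.1 might show which figure was meant, but it cannot make the visible statements agree. The link to early termination is weak: Section 3.5 lets the sponsor end the study at any time, and its reasons are only examples. The conclusion does not rely on it. The visible text also does not show what number any ethics board approved, so the point concerns the stated maximum only.

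**Conclusion.** The concern holds. The current text states two incompatible per-arm maxima, 12 and 24, and nothing visible reconciles them. The size that follows from the documents is a factor of two: 12 disputed places per arm, and an implied overall maximum of 24 or 48 if both arms are filled. The precision figures are illustrative and rest on full caps, complete evaluability and assumed interval methods. The documents do not show which number is intended, and this review does not choose one. It should be fixed because the planned size is a basic design parameter and the sample size section itself is in conflict with the Summary. It does not invalidate any planned analysis.

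**What to change.** The sponsor should:

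1. Confirm the intended maximum per arm.
2. State it identically in the Protocol Summary, Section 3 and Section 9.1, and check that the redacted number in Section 4.1 agrees.
3. If 12 is intended, confirm that the statement of sufficient information in Section 9.1 holds for 12, or revise it.

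The cost is one wording edit (the Summary) if 24 is intended, or two (Sections 3 and 9.1) if 12 is intended, plus the check of Section 4.1. No visits, procedures or extra enrolment are added. If 12 is intended, the maximum now stated in Sections 3 and 9.1 is halved. Any other study document that carries the number, which cannot be seen here, should be brought into line.
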